4.2 Determination of Sample Size

This is a proof of concept study and the number of patients chosen is based on practical considerations and not on a formal statistical power calculation. With around 90 patients randomized 2:1 to vaccination and control, it is expected that 18-month survival rate for high- and intermediate-risk mRCC patients overall can be adequately estimated for exploratory purposes but not to confirm the findings as statistical significant.

5 DATA SETS TO BE ANALYSED

The following analysis sets will be used for the statistical analysis and presentation of data:

- **The safety set:** All randomized patients with at least one safety assessment at Screening.
- **The full analysis set (FAS):** All randomized patients being evaluable for any efficacy endpoint
- **The per protocol set (PPS):** All patients randomized to Intuvax who had both doses of Intuvax administered or patient randomized to sunitinib alone, both having the nephrectomy and who continued the trial without any major protocol violations that could interfere with the objectives of this study. The criteria for PPS, regarding which protocol deviations that warrant exclusions will be determined by the following criteria.
 - Violations to inclusion, exclusion and withdrawal criteria
 - Deviations relating to primary and secondary objectives/endpoints
 - Study medication (Intuvax or Sunitinib): That was not stored and/or prepared and/or administered as defined in the protocol
 - Administration of prohibited concomitant medication
 - Availability of required data

The exact criteria that warrant exclusion from PPS will be documented in relation to review of the reported PDs. The patients excluded with reference to the PD leading to exclusion will be listed and signed off in in the *Pre-Analysis Review Form* before DBL.

The FAS is considered as the primary analysis population, and will be used for all primary and secondary efficacy analyses. The primary efficacy analysis will be repeated using the PPS. Any significant discrepancy between the results from the FAS and the PPS will be analysed and discussed.

Secondary efficacy endpoints defined as to be analyzed after start of sunitinib will be based on the subset of subjects in FAS having at least one dose of sunitinib (or as described for PFS, when subjects were included according protocol versions prior to version 4.0).

Baseline and safety will be presented using the safety set.

6 STATISTICAL AND ANALYTICAL PLANS

The planned tables and listings are presented in APPENDIX 1

6.1 Changes in the Planned Analyses

- An additional subgroup is added, see section 6.7.
- The objective and the endpoint related to evaluation of relative number of tumor infiltrating CD8+ T-cells in the resected primary tumor compared to number of infiltrating CD8+ T-cells in available diagnostic pre-biopsy (sample from either primary tumor or metastasis acceptable) will not be done. This is due to no diagnostic pre-biopsies have been available for analyses.
- Survival endpoints (primary and secondary) in this trial will be analysed using log-rank tests according to protocol, however in addition exploratory corresponding cox regressions will be applied in order to be able to estimate treatment group hazards ratios with corresponding 95% CIs, if possible. Overall analyses will include adjustment for stratification, and the results will be repeated separately by strata.

• [REDACTED]

• [REDACTED]

6.2 Blind Review

This is an open label trial, therefore any review of ongoing data that is conducted is not blind. In addition to the review of data conducted by the clinical data manager (CDM), as based on pre-defined edit checks, validation checks and manual reviews as described in the DVP, data will be reviewed ongoing during statistical programming by the statistician and statistical programmer. Findings of potential inconsistencies and/or errors in data will be reported to data management for further queries and corrections.

Any changes in the planned analysis decided in connection to the review, will be included in the final version of the SAP. Minor clarifications and/or definitions after the SAP has been finalized may be included in the *Pre-Analysis Review Form*, which will be signed before data base lock (DBL).

Classification of subjects in study populations, as defined in section 5, will be determined and documented in the *Pre-Analysis Review Form*, which will be finalized before DBL.

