13.9 Protocol Deviations

Deviations to the study protocol will be documented in a Protocol Deviation Log.

The classification of patients into protocol deviators will be made during a meeting before database lock. The classification will be mutually agreed between the Sponsor and [REDACTED] before breaking the randomization codes. Listings will indicate the allocation of patients by analysis set and the number of patients per analysis set will be recorded in the clinical study report.

Any Serious Breaches that substantially affect the integrity or the safety of the patients or the scientific validity of the study will be reported to the relevant authorities in accordance with local regulatory requirements.

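### The SAP settles analysis changes and population membership before lock in a review that is not blind, where the protocol expects classification without access to the codes

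*SAP*

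**What the plan says.** SAP 6.2 carries the title Blind Review but opens with "This is an open label trial, therefore any review of ongoing data that is conducted is not blind". Besides the data manager's checks, "data will be reviewed ongoing during statistical programming by the statistician and statistical programmer". The section then opens two routes for change. First, "Any changes in the planned analysis decided in connection to the review, will be included in the final version of the SAP". Second, "Minor clarifications and/or definitions after the SAP has been finalized may be included in the" Pre-Analysis Review Form, which is signed before database lock. The same form settles population membership: "Classification of subjects in study populations, as defined in section 5, will be determined and documented in the" form, again before lock.

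SAP 5 defines the PPS by a core (both Intuvax doses in the vaccine arm, nephrectomy in both arms, no major violation) and five headings for exclusion. It does not state the rules under those headings: "The exact criteria that warrant exclusion from PPS will be documented in relation to review of the reported PDs". The FAS is every randomized patient who can be evaluated for some efficacy endpoint. It is the primary population, and the primary analysis is repeated on the PPS.

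The protocol describes a different setting. Section 9.2 says that nobody who conducts or evaluates the trial has the randomization code until the database is locked. Section 13.9 says of the classification of deviators: "The classification will be mutually agreed between the Sponsor and [REDACTED] before breaking the randomization codes". Section 9.5 says that the study is open label.

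**The concern.** Sign-off before database lock protects against result-driven choices only if those who choose cannot yet see the results. The SAP says that the review is not blind, and neither document describes a firewall, a dataset with allocation masked, or an independent classifier. Rules that are still open at that stage could be shaped by what the data show: which deviations exclude a patient, what counts as evaluable, and which changes enter the final SAP.

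The PPS repeats the overall survival (OS) and 18-month survival analyses, and SAP 5 requires any significant discrepancy from the FAS to be analysed and discussed. If PPS membership could have been informed by outcome, that comparison loses value as a robustness check. The FAS is exposed to a lesser degree, because it also depends on a classification step taken in the same setting.

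**Working it through.** The plan gives no figure on this point, and its sample size of around 90 is not based on power (protocol 12.2, SAP 4.2). The check is therefore a comparison of the text, with one date calculation.

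1. **Timing.** Protocol 13.9 puts classification before database lock, and SAP 5 and 6.2 do the same. There is no conflict here.

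2. **Masking.** Protocol 9.2 and 13.9, read literally, describe evaluators without the code. SAP 6.2 describes evaluators who are not blind. These do not fit together. The readable items in SAP 6.1 (changes to planned analyses) do not list this as a departure; two items there are redacted.

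3. **What may be visible.** Arm is evident from the vaccination records. Deaths during the study, imaging and response are study data that may be under review. Survival after a patient's End-of-Study Visit goes to the safety database only (protocol 11.3). Protocol 7.2.1.6 turns the visit at which progression is found into the End-of-Study Visit, so deaths after progression take that route. The possible view of OS by arm is therefore partial; for progression and response it is fuller.

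4. **How much follow-up had accrued.** SAP 1 says that it is based on the protocol of 12 February 2019, so the SAP is no older than that. Protocol 7.4 plans the last visit or safety evaluation for Q3 2019, and the End-of-Study Visit is 78 weeks after screening. Taking the last visit in Q3 2019, 1 July 2019 minus 546 days is 1 January 2018, and 30 September 2019 minus 546 days is 2 April 2018. From those dates to 12 February 2019 is 407 and 316 days, or about 13 and 10 months. On planned dates, even the last patient had roughly a year of follow-up by then. The visit window and the 30-day safety evaluation shift this by some weeks.

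5. **What is fixed and what is open.** SAP 6.3.5 and 6.3.6 already fix OS censoring, the stratified log-rank test, the Kaplan-Meier 18-month estimate with its z-test, and censoring for progression-free survival and time to progression. Three things remain open:
   - the rules under the five PPS headings, two of which (deviations touching endpoints, and availability of required data) bear directly on outcome;
   - the meaning of evaluable in the FAS;
   - any change that enters the final SAP or the form.

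   For the FAS, anyone with a survival time is arguably evaluable, which would leave little room. But protocol 8.5 treats some randomized patients who withdraw early as screening failures, so the point is not settled.

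6. **What each promise covers.** Protocol 13.9 covers the classification of patients. It does not promise that analysis changes are decided blind. For those, protocol 12.1 requires the SAP to be approved before data analysis. A non-blind review during programming weakens that safeguard but does not openly breach it.

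**The case against.** The strongest reply is that the trial is open label, so code-breaking language has little meaning and the tension begins inside the protocol. Section 9.2 could be read as protecting the randomization list rather than each patient's known arm. The stated purpose of the review is to find errors and pass them to data management. No comparison of outcomes by arm is described, and no interim analysis is planned (protocol 12.4, SAP 6.9). Main methods and censoring are already specified, exclusions are listed and signed before lock, testing is exploratory without multiplicity adjustment, and the FAS is primary.

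Much of this stands, and it limits the consequence. It does not remove the conflict. Open treatment at the sites does not require an open evaluation team: this protocol masks the central CT assessor (10.4.3) and the CD8 readers (10.2.2.4) to treatment assignment. Under the narrow reading of 9.2, section 13.9 still expects classification without the codes.

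A further objection is practical. Arm cannot be fully hidden, because PPS membership depends on Intuvax dosing and only vaccinated patients have vaccination visits. That is right, and it means the remedy for classification should mask outcome rather than rely on masking arm.

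Three stronger readings are tempting but not supported:
- **The SAP admits that the codes are already broken.** It says only that review is not blind, and it puts classification before lock, as the protocol does.
- **The statistician sees results by arm.** This is an inference from the words not blind, and late survival sits in another database.
- **The PPS rules come out of the programming review.** SAP 5 ties them to the review of reported deviations, which need not be the same step, although both end in the same form.

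**Conclusion.** The point holds as a conflict between the documents and a gap in safeguards. SAP 6.2 cannot be squared with protocol 9.2 and 13.9 as written, and the exact PPS criteria and the FAS evaluability rule are not stated. Outcome-informed choices cannot be excluded for either set; nothing in the documents shows that any were made.

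The consequence is moderate, and the change should be made. The size of the bias cannot be derived. One could illustrate it by removing a few controls according to outcome, but that needs a survival rate that the documents do not give and presumes deliberate selection in a supportive analysis set, so no figure is offered.

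The conclusion assumes that not blind means allocation is accessible to the reviewers, and that no masking arrangement exists outside the two documents.

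**What to change.** - Reconcile SAP 6.2 with protocol 9.2 and 13.9, stating who has access to allocation and to outcome data before lock.
- Program the efficacy outputs on a dummy treatment variable until database lock.
- State the exact PPS exclusions and the FAS evaluability rule in the SAP.
- Classify patients from deviation listings with survival, imaging and response data removed. Accept that arm will sometimes be apparent from Intuvax dosing.
- Date every analysis change, whether in the final SAP or in the Pre-Analysis Review Form, and label as post hoc any made after arm-level outcome data were accessible.

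The cost is a little extra programming and a short addition to the SAP. Arm-specific data checks stay with the existing data management role or move to a later step.

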6.3 Hypotheses and Statistical Methods

6.3.1 Definitions

Baseline The date of randomization is defined as baseline for OS and 18-month survival rate.

The centrally assessed CT performed at the Sunitinib Start Visit is defined as CT baseline for evaluation of PFS, response rate and TTP after start of sunitinib in intermediate- and high-risk patients

The Screening Visit is defined as baseline for all other assessments than those listed above.

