This is the third Intuvax-study in man and the second study in mRCC patients. A phase I/II study in hepatocellular carcinoma patients is ongoing. Twelve (12) patients were included during 2012-2013 at one (1) study site in Sweden in the first phase I study in patients with mRCC referred for nephrectomy. The diagnosis was based on radiological presentation. No pretreatment biopsies from the kidney(s) were collected. Patients with prior autoimmune disease, with ongoing immunosuppressive therapy, or any other active cancer were

excluded. The patients' metastatic load varied. Five (5) patients were in the high-risk group and seven (7) in the intermediate group, according to the Heng prognostic model [4]. The Intuvax injections were performed with the patient hospitalized three (3) days to ensure safe care, collection of vital signs and blood samples. The vaccinations were performed twice, 14 days apart, in all patients. Nephrectomy was performed two (2) weeks after the second vaccination. Three (3) different dose levels of DCs; 5×10^6 , 10×10^6 , and 20×10^6 , were administered.

No serious adverse events (SAEs) related to the vaccination were noted. Transient fever reactions with duration less than one (1) day and rash was noted in 5 out of 12 patients. All patients survived the postoperative three (3) month follow-up visit. No significant deviations in blood chemistry attributable to the vaccination procedure were noted. Accidental bile duct injury was inflicted in one (1) patient resulting in transient hepatic failure. The renal function was decreased after nephrectomy in all patients as expected but no further decrease was observed except for one (1) patient who developed progressive renal function deterioration due to a previously undetected plasma cell disorder/myeloma. There were no signs of any autoimmune reactions as measured by standard tests while a humoral donor-specific alloimmunization was seen in three (3) patients.

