5.3 Potential Risks and Benefits

[REDACTED]

[REDACTED]	[REDACTED]
[REDACTED]	[REDACTED]
[REDACTED]	[REDACTED]
[REDACTED]	[REDACTED]
[REDACTED]	[REDACTED]
[REDACTED]	[REDACTED]

[Redacted]
	
[Redacted]

[Redacted]
	
[Redacted]

[Redacted]
	
[Redacted]

[REDACTED]	[REDACTED]
[REDACTED]	[REDACTED]
[REDACTED]	[REDACTED]

Clinical Risk/Benefit Assessment

Treatment with Intuvax immunotherapy might potentially result in prolonged survival. The risk of serious immunologic reactions is expected to be low considering data from the supporting animal studies that have been performed and the completed phase I study in mRCC patients and the ongoing phase I study in HCC patients. The risk for a serious late immune reaction with secondary organ damage (most probably in the remaining kidney) is expected to be low considering the results from the same studies.

Intuvax-induced alloimmunization does not jeopardize future RBC transfusions, since RBC lack HLA antigen expression. Moreover, there is a very low risk that mRCC patients on sunitinib treatment will require platelet-transfusions or will be transplanted with an allogeneic organ. However, if severe thrombocytopenia occurs in patients that have developed HLA-antibodies due to prior Intuvax treatment, platelet transfusion can be conducted by selecting HLA-matched platelet donors. As treatment with Intuvax, followed by sunitinib, might prolong the survival in a patient population with poor prognosis, Immunicum believe the risk benefit overview is well balanced.

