12.1.13 Other Safety Assessments

Physical Examination

Physical examination data will be summarized by visit and treatment group as described in *Section 12.1.4*.

Vital Signs

Vital signs will be summarized by visit and treatment group, together with changes from Screening as described in *Section 12.1.4*.

Vital signs assessed during vaccination, will be summarized both by nominal time point and as change from the pre-vaccination at each post-vaccination time point.

Laboratory Safety Assessments

For laboratory data, summary statistics will be produced for observed values and for changes from screening to each visit as described in *Section 12.1.4*. In addition, the number of abnormal and clinically significant observations will be tabulated for each treatment group by visit. Abnormal values will be flagged in listings.

Shift tables will show the number of patients who changed from below, within or above the reference range at Screening to below, within or above the reference range at each time of assessment.

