6.3.11 Other Safety Assessments

Vital Signs

For vital signs parameters (systolic and diastolic blood pressure, supine heart rate and temperature) summary statistics will be produced for observed values by visit. In addition, the difference from baseline to each visit at which they were assessed will be derived and presented.

Vital signs assessed at time points post vaccination will be summarised separately.

Clinical Laboratory Measurements

The laboratory categories are Hematology, Clinical Chemistry, Coagulation, Urine analysis and Pregnancy analysis.

For all laboratory parameters, summary statistics will be produced for observed values by visit. In addition, the difference from baseline to each visit at which they were assessed will be derived and presented. The number of abnormal (low and high) and clinically significant observations will be tabulated for each treatment group by visit. Abnormal values will be flagged in listings.

Shift tables that show the number of patients who changed from low, normal or high at baseline to low, normal or high at each post-baseline time of assessment will be presented.

Physical Examination

Physical examination results will be tabulated including number of subjects with normal, abnormal not clinically significant or clinically significant abnormalities by visit. Corresponding shift tables for changes from baseline will be presented, and all the results will be listed.

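### Renal change and shift tables run from the pre-nephrectomy Screening value only; a supplementary post-nephrectomy comparison by arm would show any further decline directly

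*SAP*

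**What the plan says.** SAP 6.3.1 sets randomization as baseline for survival and the Sun-Start CT as baseline for the imaging endpoints. For the rest: "The Screening Visit is defined as baseline for all other assessments than those listed above". For laboratory parameters, SAP 6.3.11 plans that "the difference from baseline to each visit at which they were assessed will be derived and presented", together with "Shift tables that show the number of patients who changed from low, normal or high at baseline to low, normal or high" at later assessments. Protocol 12.1.13 agrees: "summary statistics will be produced for observed values and for changes from screening to each visit", with shift tables also starting at Screening. SAP 6.3.11 adds a summary of levels: "For all laboratory parameters, summary statistics will be produced for observed values by visit".

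On renal risk, Protocol 5.3 refers to "The risk for a serious late immune reaction with secondary organ damage (most probably in the remaining kidney" and expects it to be low. On phase I, Protocol 5.1 reports: "The renal function was decreased after nephrectomy in all patients as expected but no further decrease was observed", apart from one patient whose progressive deterioration was put down to a previously undetected plasma cell disorder.

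On timing, the Protocol flow chart (Table 2, note a) places the Nephrectomy Visit laboratory samples before surgery. The first scheduled sample after surgery is at Sun-Start, five to eight weeks later. Protocol Table 7 (note b) has GFR measured at Screening, Sun-Start and every later visit.

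**The concern.** The renal question raised by the protocol concerns what happens after surgery: once function has fallen because a kidney was removed, does the remaining kidney lose more in vaccinated patients? Protocol 5.1 used that distinction for phase I, and relied on it in arguing that the immune response was tumor-specific. The readable text of the present plan includes no within-patient change from a post-nephrectomy value, although the values are collected.

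This has two consequences. A change from Screening at any follow-up visit is the surgical step plus the later change, so the between-patient spread of the step is added to every later result. In the shift table, a patient whom surgery moves from normal to high creatinine is already in that cell at Sun-Start and stays there however far the remaining kidney worsens. What is at stake is how clearly a secondary, descriptive safety objective addresses a risk that the protocol itself names.

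**Working it through.** The documents give no renal SD, effect size or power figure, so there is no stated result to reproduce. The check has four parts.

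**1. Is a post-surgery baseline available?** Yes. Using the visit windows in Protocol 7.2.1 and Table 2, Sun-Start falls at the earliest 3 + 35 = 38 days after the second vaccination. At the latest it falls (63 − 16) + 56 = 103 days after it.

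**2. Cost in precision of starting from Screening.** About 90 patients at 2:1 gives 60 and 30, so SE = SD × √(1/60 + 1/30) = SD × 0.2236. Let s be the SD of the surgical GFR change and l the SD of the later change, in mL/min (both assumed), with correlation ρ. Then SD from Screening = √(s² + l² + 2ρsl), and SD from Sun-Start = l. With ρ = 0:

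| s | l | SE from Screening | SE from Sun-Start | Ratio | ρ at which ratio = 1 |
|---|---|---|---|---|---|
| 6 | 6 | 1.90 | 1.34 | 1.41 | −0.50 |
| 6 | 10 | 2.61 | 2.24 | 1.17 | −0.30 |
| 10 | 6 | 2.61 | 1.34 | 1.94 | −0.83 |
| 10 | 10 | 3.16 | 2.24 | 1.41 | −0.50 |
| 15 | 6 | 3.61 | 1.34 | 2.69 | not attainable |
| 15 | 10 | 4.03 | 2.24 | 1.80 | −0.75 |

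The last column is ρ = −s/(2l). For s = 6, l = 10 and ρ = −0.3, the SD from Screening is √(36 + 100 − 36) = 10, equal to that from Sun-Start. Negative correlation is plausible: partial recovery would produce it, and so would measurement error in the Sun-Start value, which enters the two changes with opposite signs.

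**3. Shift-table saturation.** Assume a GFR limit of 60, a Screening mean of 80 to 90 (SD 18), a surgical loss of 20 to 30 (SD 10) and a later SD of 7. By simulation, 28% to 64% of patients normal at Screening are already low at Sun-Start from surgery alone, and a further fall cannot move them. Starting the shift table at Sun-Start does not cure this. On the same assumptions, only 31% to 69% of all patients are normal at Sun-Start, so the other 31% to 69% are low and still cannot move further. The three-category scale is the limit. On a continuous scale, an extra individual loss of 15 is 15/√(10² + 7²) = 1.2 SD measured from Screening and 15/7 = 2.1 SD measured from Sun-Start.

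**4. Means and a rare reaction.** One patient in 60 losing 40 mL/min moves the arm mean by 40/60 = 0.67 under either baseline. The chance of at least one case among 60 vaccinated patients, 1 − (1 − p)^60, is 45%, 70% and 95% for true rates of 1%, 2% and 5%. A worst-change summary per patient is therefore more useful than means alone.

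**The case against.** The case for leaving the plan alone is substantial. Screening is the conventional pre-treatment baseline, is common to both arms, and is what the protocol specifies. Both arms have nephrectomy and results are given by treatment group, so the surgical step cancels on average.

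A reader might infer that the planned tables mask a late renal reaction, or cannot show one at all. The documents do not support that. Levels at Sun-Start and each later visit appear side by side by arm in Table 14.3.4.3. For the same patients, mean change from Screening at a later visit minus that at Sun-Start equals the mean change since Sun-Start. Individual values are listed (16.2.8.1), abnormal and clinically significant values are counted by visit, and clinically significant findings are reported as adverse events (Protocol 11.2).

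These routes stand, but they are partial. The observed-value tables are group-level and give neither the spread nor the extremes of within-patient change. Follow-up visits stop at locally verified progression, so later visits describe a selected set. SAP 6.3.2 applies LOCF to assessments evaluated by visit; if that covers laboratory data, a pre-nephrectomy value could be carried into later visits. Listings and adverse events work case by case.

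A reader might also infer that Sun-Start should replace Screening. It should not. Sun-Start is after randomization and vaccination, so it absorbs any earlier injury and omits patients who never reach it. Sunitinib also starts there.

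Finally, no between-arm laboratory test is planned, so the standard-error ratio alters no planned inference.

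**Conclusion.** The point holds as a low-cost improvement. The Screening-based change and shift tables combine expected nephrectomy loss with later loss. They dilute, without biasing, the by-arm view of further decline in the remaining kidney, and no planned table isolates that decline within patients.

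The gain in precision from a Sun-Start comparison, about 1.2 to 2.7 times in standard error, rests on assumed SDs and on no correlation between surgical and later change; it could be smaller or absent. The 28% to 64% saturation figure is likewise illustrative. The finding that a patient already beyond a limit cannot move further in a three-category table needs no numerical assumption.

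The detailed risk material in Protocol 5.3 is redacted, so any renal-specific handling there cannot be judged. Primary results are unaffected.

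**What to change.** Keep all Screening-based tables at every visit, as Protocol 12.1.13 requires. In SAP 6.3.11 and Table 14.3.4.3 add, by treatment arm and without LOCF:

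- within-patient change from Sun-Start to each later visit, for creatinine and GFR;
- worst within-patient change after Sun-Start, on a continuous or percent scale, for creatinine and GFR;
- the same two presentations for U-microalbumin and U-red blood cells.

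For intermediate-risk patients enrolled before protocol version 4.0, use the first laboratory visit after nephrectomy in place of Sun-Start. This parallels the SAP 6.3.6 rule for PFS. Do not rely on a three-category shift from Sun-Start.

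State in the SAP that these tables are supplementary and why: the starting point is post-randomization and post-vaccination, patients who never reach it are absent, and sunitinib begins at that visit. They must be read by arm alongside the Screening-based tables.

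The cost is a paragraph of SAP text and a few tables. No new data are needed.
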